6.2.7.1 Primary and Key Secondary Efficacy Analyses

6.2.7.1.1 Primary Efficacy Analyses

The primary efficacy endpoint, occurrence of SVN, is a binary response variable (Yes, No). It will be summarized using descriptive statistics by treatment group and will be analyzed to compare trilaciclib and placebo using modified Poisson regression (Zou, 2004) to account for the variable duration of the induction treatment period for each patient. The model will include baseline ANC as a covariate, the stratification factors of ECOG (0 or 1 vs. 2) and brain metastases (Yes vs. No), and treatment as a fixed effect. The logarithm transformation of number of induction cycles will be included as an offset variable in the modeling. The two-sided p-value, adjusted rate ratio (aRR) (trilaciclib vs placebo) and its 95% CIs will be presented.

For the other primary efficacy endpoint, DSN in Cycle 1 based on Strategy 1 in [Section 5.1.1.2.1](#), treatment difference will be evaluated using a nonparametric analysis of covariance

(ANCOVA) (Stokes 2012). The nonparametric ANCOVA will include study baseline ANC value as covariate, stratification factors of ECOG (0 or 1 vs. 2) and brain metastases (Yes vs. No), and treatment as a fixed effect. A two-sided p-value will be generated from this model. Along with the descriptive statistics, the mean difference and Hodges-Lehmann estimate of median difference between the two treatment groups, together with its 95% CIs will be provided. Additionally, DSN for each cycle will be presented using descriptive statistics.

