The intent-to-treat (ITT) population includes all randomized patients and will be the primary analysis set for efficacy and [REDACTED]. ITT analyses will be conducted on the basis of the assigned treatment. The safety analysis set includes all patients who received at least 1 dose of study drug and will be used for the analysis of safety endpoints. The safety analysis set analyses will be conducted on the basis of the actual treatment received. The PK analysis set will include all dosed patients in the PK portion of the study with evaluable PK data.

Data will be summarized by treatment group. Treatment differences between treatment groups will be calculated as trilaciclib + E/P/A therapy versus placebo + E/P/A therapy. The descriptive summary for the categorical variables will include counts and percentages. The descriptive summary for the continuous variables will include means, medians, standard deviations, and minimum and maximum values.

Study G1T28-05 was originally designed as a Phase 2 clinical study to investigate if myelopreservation, ie, preservation of hematopoietic stem and progenitor cell (HSPC) and immune system function during chemotherapy, by trilaciclib could provide survival benefit to patients receiving a combination of cytotoxic chemotherapy and an immune checkpoint inhibitor. Recent results from a clinical study in treatment-naïve extensive-stage SCLC patients (Study G1T28-02) who received trilaciclib or placebo in combination with etoposide/carboplatin, provided compelling evidence that trilaciclib resulted in a clinically meaningful decrease in myelosuppression across 3 lineages: neutrophils, RBC, and lymphocytes. Hence, the primary analysis in this Study G1T28-05, where the chemotherapy backbone of etoposide and carboplatin is the same as Study G1T28-02, is being modified to assess primary and key secondary myelosuppression efficacy endpoints. This allows for an earlier assessment of trilaciclib's mechanism of action (MOA) and efficacy, with OS retained as a secondary endpoint. This change in endpoints does not alter the assessments or protocol-defined patient care.

The primary endpoints include (i) duration of severe (Grade 4) neutropenia in Cycle 1 and (ii) occurrence of severe (Grade 4) neutropenia. Occurrence will be displayed as the proportion of patients with an event for each study arm.

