#### 13.5.1.1. Methods of Analysis for Primary Myelosuppression Efficacy Endpoints

A 2-sided p-value will be calculated for the DSN in Cycle 1 using nonparametric analysis of covariance (ANCOVA) (Stokes 2012). The nonparametric ANCOVA will include study baseline ANC value as covariate, stratification factors of ECOG performance status (0 to 1 versus 2) and presence of brain metastases (yes versus no), and treatment as a fixed effect. Along with the descriptive statistics, the Hodges-Lehmann estimate of median difference between the 2 treatment groups, together with its 95% CIs will be provided.

The occurrence of severe (Grade 4) neutropenia is a binary response variable (yes versus no) and will be analysed to compare trilaciclib and placebo using modified Poisson regression (Zou 2004) to account for the variable duration of the induction treatment period for each patient. The model will include baseline value as covariate, the stratification factors of ECOG performance status (0 to 1 versus 2) and presence of brain metastases (yes versus no), and treatment as a fixed effect. The 1-sided p-value adjusted relative risk (aRR) (trilaciclib vs placebo) and its 95% CIs will be presented.

A detailed description of the analysis methods will be provided in the SAPs.

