2.3. Number of Patients

Overall, approximately 100 patients will be enrolled in the study. The 100 patients will be randomly assigned (1:1 fashion) to trilaciclib 240 mg/m² or placebo administered IV on Days 1 to 3 with E/P/A therapy for up to four 21-day cycles (induction part).

The initial sample size calculations were based on a primary endpoint of OS where a sample size of 100 (1:1 treatment allocation ratio between the two groups of placebo + E/P/A and trilaciclib + E/P/A) provided 80% power to detect a hazard ratio of 0.6 using an overall type 1 error probability of 0.1 (1-sided). With the change in endpoints outlined in amendment 2, the sample size calculation is now based on demonstrating the superiority of trilaciclib + E/P/A versus placebo + E/P/A with respect to at least one of the primary endpoints. With this amendment, the overall type I error rate is now 0.025 (1-sided) and the type II error rate used to compute sample size is 0.10 (corresponding to 90% power).

To maintain the overall type I error rate, by using the most conservative Bonferroni procedure for the 2 primary endpoints, a 1-sided individualized type I error rate $0.025/2 = 0.0125$ is assigned to each outcome variable in the sample size calculation. Assuming a common standard deviation of 2.5, a true difference in the duration of severe (Grade 4) neutropenia in Cycle 1 of at least 2 days between the treatment groups (trilaciclib + E/P/A versus placebo + E/P/A) requires 82 evaluable patients (41 per treatment arm). This implies that 88 patients need to be randomized assuming a 95% evaluability rate. For occurrence endpoints (occurrence of severe (Grade 4) neutropenia, assuming its proportion of 45% for placebo + E/P/A, testing for an absolute reduction of 34% to 11% with trilaciclib + E/P/A would require a sample size of at least 100 patients (50 per treatment arm). Assuming a 95% evaluability rate, at least 106 patients need to be enrolled to complete the study. Therefore, the final adjusted sample size is 106 to account for the evaluation of 2 primary endpoints.

All calculations were carried out using the POWER procedure in SAS® version 9.4.

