4. PROSPECTIVELY DEFINED ANALYSES

As outlined in the protocol, trilaciclib is an IV cyclin dependent kinase (CDK) 4/6 inhibitor being evaluated for its ability to decrease chemotherapy-induced myelosuppression when administered in combination with cytotoxic chemotherapy. Unlike granulocyte-colony stimulating factor (GCSF), which stimulates production of neutrophils, and transfusions, which only replace red blood cell (RBC) or platelets, trilaciclib is hypothesized to facilitate myelopreservation of all hematopoietic lineages including neutrophils, RBC, platelets, lymphocytes, etc.

To capture the potential for multilineage trilaciclib benefit, the following analyses are prospectively proposed in Table 3 and their associated endpoint derivation and analysis methods will be detailed in Sections 5.1 and 6.2.7 with the multiplicity adjustments described in Section 6.2.7.1.4.

Table 3 Prospectively Defined Analyses

Occurrence (proportion of patients) of severe (Grade 4) neutropenia
Duration of severe (Grade 4) neutropenia in Cycle 1
Occurrence (proportion of patients) of RBC transfusions on/after 5 weeks
Occurrence (proportion of patients) of GCSF administration
Cumulative incidence of major adverse hematologic events (MAHE) which is defined to include components as the following: 
 • All-cause hospitalizations • All-cause dose reductions • Febrile neutropenia • RBC transfusions on/after 5 weeks • Prolonged severe (Grade 4) neutropenia (duration > 5 days)
All-cause hospitalizations in the MAHE composite
All-cause dose reductions in the MAHE composite
Febrile neutropenia in the MAHE composite
RBC transfusions on/after 5 weeks in the MAHE composite
Prolonged severe (Grade 4) neutropenia in the MAHE composite

RBC = Red Blood Cell; GCSF = granulocyte-colony stimulating factor;

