5. PRIMARY AND SECONDARY ENDPOINTS

The following general definitions will be applied to all endpoints derivation unless otherwise specified.

Term	Definition
Severe Neutropenia (SVN)	ANC lab value that meets the common terminology criteria for adverse events (CTCAE) criteria for \geq Grade 4 toxicity
Cycle baseline	The last non-missing value within the window starting from 3 days prior to the date/time of study drug administration on Day 1 of Cycle 1 and 1 day prior to Day 1 of each subsequent cycle (i.e. Cycle 2, Cycle 3, etc.); must be prior to the time of study drug administration
Cycle nadir	The lowest value for a given hematologic parameter that occurs between start of cycle and end of cycle and is less than the cycle baseline.
Duration of cycle	Total number of days from start of cycle to end of cycle, that is, date of end of a cycle - date of start of cycle + 1.
End of cycle*	Day 1 of the subsequent cycle. For example, the end of cycle for Cycle 1 is Day 1 of Cycle 2. For the last induction cycle (where no subsequent maintenance cycle is given), the end of cycle will be defined as Day 36 after the first dose of the cycle. For the last maintenance cycle, the end of cycle will be defined as Day 30 after the first dose of the cycle.
Start of cycle	Day 1 of each cycle starts with the administration of study drug(s) (etoposide, carboplatin, atezolizumab, or trilaciclib)
Start of study	Date of randomization
Study baseline	The last non-missing value prior to, or on the date of administration of study drug(s) (etoposide, carboplatin, atezolizumab, or trilaciclib); must be prior to the time of study drug administration
Change from baseline	Calculated as the post-baseline value minus the baseline value. If the baseline value is missing for a particular endpoint, change from baseline will be missing.
Induction treatment period	Between the date of randomization and end of cycle for the last Induction cycle.
Maintenance treatment period	Between the date of Day 1 of the first maintenance cycle and end of cycle for the last Maintenance cycle.
Overall treatment period	Between the date of randomization and end of cycle for the last cycle.

* For various hematologic parameter analyses, the last assessment prior to end of cycle will be utilized in the analyses. Situations where this applies will be indicated as such.

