5.1.2. Key Secondary Endpoints

5.1.2.1. Occurrence of RBC Transfusions

Each RBC transfusion with a unique start date on/after 5 weeks on study during the induction treatment period will be defined as a separate event and included in the efficacy analyses. A sensitivity analysis including all events occurring during the entire induction treatment period will also be performed.

Occurrence of an RBC transfusion during the induction treatment period is defined as a binary variable (Yes or No); Yes if total number of RBC transfusion ≥ 1 is observed, No for other scenarios.

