6.2.7.1.2 Key Secondary Efficacy Analyses

Occurrence of RBC transfusions on/after 5 weeks on study is a binary variable and will be summarized using the same method for occurrence of SVN described in [Section 6.2.7.1.1](#) except baseline HGB will be used as a covariate instead of baseline ANC in the modified Poisson model. Also, the offset will be the logarithm transformation of duration of induction treatment period divided by 7 (i.e. week) instead of number of induction cycles, and. An additional sensitivity analysis will look all transfusions during the induction treatment period, and all transfusions with a subset of subjects completing at least 1 cycle.

Occurrence of GCSF administration is a binary variable and will be summarized using the same method for occurrence of SVN described in [Section 6.2.7.1.1](#).

All-cause dose reductions will be analyzed to compare trilaciclib and placebo using a negative binomial regression model to account for the potential over-dispersion. The model includes the stratification factors of ECOG (0 or 1 vs. 2) and brain metastases (Yes vs. No), and treatment as a fixed effect. The logarithm transformation of number of induction cycles will be included as an offset variable in the modeling. The two-sided p-value, aRR (trilaciclib vs placebo) and its 95% CIs will be presented.

The total number of all-cause dose reductions will be summarized descriptively, along with the number of induction cycles, and the event rate per cycle (calculated as the total number of events/total number of induction cycles). The cumulative incidence of events during the induction treatment period will be summarized and presented graphically by cycle.

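### The exposure offsets make the confirmatory Yes/No models estimate something other than the stated proportion of patients, most clearly for RBC transfusion, where the offset counts five weeks in which no event can qualify

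*SAP*

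**What the plan says.** **Endpoints.** SAP Section 4, Table 3 lists "Occurrence (proportion of patients) of severe (Grade 4) neutropenia" and describes RBC transfusion and G-CSF use in the same way. SAP 5.1.1.1, 5.1.2.1 and 5.1.2.2 reduce each to one Yes/No per patient over induction. The protocol synopsis adds: "Occurrence will be displayed as the proportion of patients with an event for each study arm". SAP 2.3 sizes SVN on proportions: "assuming its proportion of 45% for placebo + E/P/A, testing for an absolute reduction of 34% to 11% with trilaciclib + E/P/A".

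**Models.** SAP 6.2.7.1.1 fits modified Poisson regression to SVN, gives variable induction length as the reason, specifies that "The logarithm transformation of number of induction cycles will be included as an offset variable in the modeling", and calls the result a rate ratio. SAP 6.2.7.1.2 uses the same model for G-CSF. For RBC transfusion, "the offset will be the logarithm transformation of duration of induction treatment period divided by 7 (i.e. week) instead of number of induction cycles". The protocol (13.5.1.1) names the effect measure differently: "The 1-sided p-value adjusted relative risk (aRR) (trilaciclib vs placebo) and its 95% CIs will be presented".

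**Windows.** What counts for RBC is "Each RBC transfusion with a unique start date on/after 5 weeks on study during the induction treatment period" (SAP 5.1.2.1). The induction treatment period, which supplies the offset, is "Between the date of randomization and end of cycle for the last Induction cycle" (SAP Section 5).

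**Undosed patients.** SAP 3.2 keeps randomized but untreated patients in the ITT set, the primary efficacy set (3.1.1). Under 5.2.1.2 a cycle starts only with a dose.

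**Role.** SAP 6.2.7 rests the efficacy claim on the multiplicity-adjusted one-sided p-values. In 6.2.7.1.4, SVN is H2, RBC transfusion is H4 and G-CSF is H5.

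**The concern.** An offset belongs with a count that can keep growing with exposure. Here the response stops at one, while cycles or weeks continue to accumulate after the event. A patient with SVN in Cycle 1 who completes four cycles contributes one event over four cycles; a patient who stops after Cycle 1 contributes one over one. The model therefore compares patients-with-event per cycle or week, not proportions of patients.

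Induction length is observed after randomization and treatment may affect it. If the arms differ in exposure, the confirmatory estimate moves for that reason alone. For RBC transfusion the denominator also includes the first five weeks, when nothing can qualify, so the result is not a rate over time at risk either. Finally, a cycle offset cannot accommodate a patient with zero cycles, so the SVN and G-CSF analyses would lose ITT patients without the SAP saying so.

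**Working it through.** **1. The plan's own figure.** For 45% vs 11%, one-sided 0.0125 and 90% power, a Wald calculation on the log odds ratio gives 50 per arm, the stated 100 in total. Pooled, Fisher exact and continuity-corrected formulas give 41, 46 and 47. Then 100/0.95 = 105.3, rounded up to 106. The inputs are plain proportions with no exposure term.

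**2. What the offset does.** With treatment only in the model, the fitted ratio is (events_T / total exposure_T) ÷ (events_P / total exposure_P) = risk ratio × (mean exposure_P / mean exposure_T). This is exact without covariates and approximate with them.

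**3. Assumed exposure** (the documents give none). Probabilities of receiving 1, 2, 3 or 4 cycles:
- Pattern A: 0.04, 0.04, 0.04, 0.88; mean 3.76 cycles.
- Pattern B: 0.12, 0.10, 0.08, 0.70; mean 3.36 cycles.
- Weeks for 1, 2, 3 or 4 cycles taken as 5, 8, 11 and 12. Mean A = 0.20 + 0.32 + 0.44 + 10.56 = 11.52; mean B = 0.60 + 0.80 + 0.88 + 8.40 = 10.68.

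Unless stated otherwise, trilaciclib follows A and placebo B.

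**4. SVN.**
- 45% in both arms, all in Cycle 1: ratio 3.36/3.76 = 0.89; with exposures reversed, 1.12; with equal exposure, 1.00.
- One-sided rejection in favour of trilaciclib (z < -1.96, treatment-only model, robust variance, 53 per arm, 40,000 trials): about 7% with the offset vs 2% without. Reversed: about 0.6% vs 2%. Equal exposure: about 2.3% vs 2%.
- Constant 15% risk per cycle: proportions 0.453 vs 0.411, so 1.10 without the offset and 1.10 × 0.894 = 0.98 with it.
- Design case 45% vs 11%: power 99% with the offset and 98% without; with exposures reversed, 95% and 98%.

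**5. RBC transfusion**, weekly hazard 0.04 after Week 5 in both arms.
- Proportions 0.228 vs 0.199; ratio 1.14.
- SAP offset: (0.228/11.52) ÷ (0.199/10.68) = 1.06. Hazards from 0.02 to 0.08 also give 1.06; reversed exposure gives 0.94.
- At-risk weeks (weeks minus 5, means 6.52 and 5.68): (0.228/6.52) ÷ (0.199/5.68) = 1.00. This leaves out the one-cycle patients, 4% vs 12%.
- At equal exposure all three ratios are 1.00.
- Power at 5.7% vs 21.6%, the G1T28-02 figures in protocol 4.3.1, for one test at one-sided 0.025: 58% without the offset. With it: 58% at equal exposure, 65% if trilaciclib patients stay longer, 51% if placebo patients do.

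The protocol says Week 5, which could mean four completed weeks; the dead time would then be four weeks.

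**6. G-CSF**, 10% per cycle from Cycle 2 in both arms. Protocol 8.6 bars growth factors in Cycle 1; 8.4.5.2 allows an exception for high-risk febrile neutropenia. Proportions 0.250 vs 0.215: 1.16 without the offset, 1.04 per cycle, 1.00 per cycle from Cycle 2.

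**7. Undosed patients.** Zero cycles gives log(0), which is minus infinity, and a test fit failed. For RBC transfusion there is no last induction cycle, so the duration is undefined rather than zero. Study baseline is also defined relative to dosing (SAP Section 5), so removing the offset alone may not keep these patients in. Even if every non-evaluable patient under the 95% assumption were undosed, that is about 5 of 106 (0.05 × 106 = 5.3).

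**The case against.** The offset is deliberate. Both documents choose modified Poisson to handle variable induction length, the SAP labels the result a rate ratio, and protocol Section 13 lets the SAP prevail. A reader might take the protocol's relative-risk label as proof that a risk ratio was intended. It is not: protocol 13.5.2.2 uses the same label for the negative binomial MAHE count model, so the term is loose. SAP Section 7, which lists changes from the protocol, is blacked out and may address the label.

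Dropping the offset is not neutral either. Under equal hazards it makes the arm that stays longer look worse (1.10 for SVN, 1.14 for RBC, 1.16 for G-CSF). For SVN and G-CSF the choice is therefore partly one of estimand.

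Safeguards exist: stratified CMH and tipping-point analyses without an offset and an mITT repeat (SAP 6.2.7.1.5), and an RBC analysis of all induction transfusions (5.1.2.1, 6.2.7.1.2), in which event and exposure windows coincide. SAP 6.1.2 excludes missing efficacy data in general, though it does not name zero cycles. The size shown depends on assumed exposures: an average cycle delay of 0.9 week among placebo patients reaching Cycle 2 would bring the RBC ratio from 1.06 to about 1.02.

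All of this limits the point. It does not answer it for RBC transfusion, where the offset window and the event window disagree by definition, and none of the safeguards feeds the gatekeeping p-values.

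**Conclusion.** The point holds as an estimand mismatch that should be fixed. The three confirmatory models do not estimate the proportion of patients unless induction exposure is equal between arms. For H4 the fault is clearest: the RBC model yields neither a ratio of proportions nor a rate over time at risk. The unstated zero-cycle rule is a smaller gap, probably affecting few patients.

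Two stronger readings are not supported. One is that the trial's type I error is inflated. It is not when treatment leaves exposure unchanged. The 7% figure for SVN needs treatment to change exposure but not neutropenia; H1 is then also null, and in 20,000 simulated trials of that scenario H1 and H2 were both rejected in 2.2%. The other is that the SVN conclusion is at risk; at 45% vs 11% it would hardly change.

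The practical effect is on H4 and H5, tested only after H1 and H2 are rejected. The sizes rest on assumed exposure patterns and hazards, and the direction depends on which arm receives more induction treatment.

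**What to change.** - In SAP 6.2.7.1.2, make modified Poisson without an offset (adjusted relative risk) confirmatory for RBC transfusion. Preferably do the same for SVN (6.2.7.1.1) and G-CSF, so that the model matches the stated proportion.
- Keep the offset models as sensitivity analyses labelled rate ratio. Any RBC rate model should count only time from Week 5 and remain a sensitivity analysis, because it excludes patients on a post-randomization condition.
- Keep undosed ITT patients in the model, with the last pre-randomization ANC or hemoglobin as baseline and the outcome set to No.

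The cost is SAP wording and one model option. No new data are needed, and N stays at 106 because the sizing already uses proportions. The downside is that the main estimate no longer adjusts for unequal induction length, so patients who stop early without an event count as No. The retained offset model and the planned tipping-point analysis cover that.

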6.2.7.1.2 Key Secondary Efficacy Analyses

Occurrence of RBC transfusions on/after 5 weeks on study is a binary variable and will be summarized using the same method for occurrence of SVN described in [Section 6.2.7.1.1](#) except baseline HGB will be used as a covariate instead of baseline ANC in the modified Poisson model. Also, the offset will be the logarithm transformation of duration of induction treatment period divided by 7 (i.e. week) instead of number of induction cycles, and. An additional sensitivity analysis will look all transfusions during the induction treatment period, and all transfusions with a subset of subjects completing at least 1 cycle.

Occurrence of GCSF administration is a binary variable and will be summarized using the same method for occurrence of SVN described in [Section 6.2.7.1.1](#).

All-cause dose reductions will be analyzed to compare trilaciclib and placebo using a negative binomial regression model to account for the potential over-dispersion. The model includes the stratification factors of ECOG (0 or 1 vs. 2) and brain metastases (Yes vs. No), and treatment as a fixed effect. The logarithm transformation of number of induction cycles will be included as an offset variable in the modeling. The two-sided p-value, aRR (trilaciclib vs placebo) and its 95% CIs will be presented.

The total number of all-cause dose reductions will be summarized descriptively, along with the number of induction cycles, and the event rate per cycle (calculated as the total number of events/total number of induction cycles). The cumulative incidence of events during the induction treatment period will be summarized and presented graphically by cycle.

